5.2 Study Points of Reference

Baseline

The baseline measurement is defined as the last measurement prior to the first dose of IP. If the measurement is taken on the same day as the first dose and the exact measurement time relative to the first dose is unknown, it will be assumed to have been taken prior to the first dose of IP. If a subject does not receive IP, baseline is the closest recorded measurement on or prior to the randomization date. For baseline duplicate BMD taken on the same day, the baseline is obtained as the average of the measurements.

Note: If baseline result from DXA assessment is not available, the result assessed on or before Study Day 14 will be considered baseline.

Study Day 1

The first day of IP administration or the day of randomization for subjects who do not receive any dose of IP.

Study Day

The number of days from Study Day 1, inclusive:

Study Day = (Date of Interest – Date of Study Day 1) + 1

For days prior to Study Day 1:

Study Day = (Date of Interest – Date of Study Day 1)

Analysis Visit

To allow for variations in scheduling study visits, the analysis visit windows defined in [Appendix A](#) will be used to assign evaluations to the most appropriate nominal visit for analysis and summarization.

5.3 Study Dates

Enrollment (Randomization) Date

The date on which a subject is assigned to one of the treatments through IVRS.

First Dose Date

The date of administration of the first dose of IP; this may or may not be the same as the randomization date.

Last Dose Date

The date of administration of last dose of IP

Study Day 1

Study day 1 is defined as the first dose date. For subjects who did not receive IP, study day 1 is defined as the randomization date.

End of the 6-Month Treatment Period Date

The end of the 6-month treatment period date is defined as the date of the last assessment at the Month 6 visit. For subjects who discontinue from the study before completing the Month 6 visit, the end of study date is used for the end of the 6-month treatment period end date. For those subjects who missed the Month 6 visit but did not terminate the study early, the target day (Day 183) for Month 6 plus 3 days will be used as the end of the 6-month treatment period date.

Start of the Follow-up Period Date

The start of the follow-up period date is defined as the end of the 6-month treatment period date plus one day.

End of the Follow-up Period Date

For subjects with non-missing start of the follow-up period date, the end of the follow-up period date is defined as the end of study date as recorded on the electronic case report form (CRF).

5.4 Study Time Intervals

Screening Period

The time period between the date of informed consent and first dose of IP or randomization date for subjects who do not receive IP.

Treatment Period

The time period from the first dose date to the end of the 6-month treatment period date inclusive.

Follow-up Period

For subjects entering in the 3-month follow-up period: the time period from the start of follow-up period date to the end of study date.

5.5 Subject Disposition

Enrolled

Individuals are considered enrolled if they have been assigned a randomization number. Enrolled individuals are referred to as subjects.

Exposed to IP

Subjects are considered exposed to IP if they have a value for the sum of IP volume that exceeds zero.

5.6 Arithmetic Calculations

Percent Change from Baseline

The change from baseline value divided by the baseline value and multiplied by 100:
$$((\text{value at date of interest} - \text{baseline value}) / \text{baseline value}) * 100.$$

Subject Incidence for AEs

The subject incidence for a given event in a given time period is defined as the number of subjects with at least 1 reported occurrence of the event divided by the number of subjects who are at risk for having the event at the beginning of the given time period. For subjects with multiple occurrences of the same event, the event will only be counted once per subject.

6. Analysis Sets

6.1 Full Analysis Set

The full analysis set includes all randomized subjects. Subjects in this set will be analyzed according to their randomized treatment assignment, regardless of treatment received.

6.1.1 Primary Efficacy Analysis Subset

The primary efficacy analysis subset will include all randomized subjects who have a baseline lumbar spine DXA BMD measurement and at least 1 post-baseline lumbar spine DXA BMD measurement. Data from subjects in this subset will be analyzed according to randomized treatment groups, regardless of treatment received.

6.1.2 Hip Bone Mineral Density Efficacy Analysis Subset

The hip BMD analysis subset will include all randomized subjects who have a baseline hip DXA BMD measurement and at least 1 post-baseline hip DXA BMD measurement. Data from subjects in this subset will be analyzed according to randomized treatment groups, regardless of treatment received.

6.1.3 Bone Turnover Marker Analysis Subset

The bone turnover marker analysis subset will include all randomized subjects who have a baseline BTM measurement of interest and at least 1 post-baseline BTM measurement of interest. Data from subjects in this subset will be analyzed according to randomized treatment groups, regardless of treatment received.

6.2 Safety Analysis Subset

The safety analysis subset will include all randomized subjects who receive at least 1 dose of IP. These subjects will be analyzed according to their actual treatment received, such that subjects who received at least 1 dose of the romosozumab self-administration by AI/Pen will be analyzed in the romosozumab self-administration by AI/Pen treatment group, regardless of the randomized treatment.

6.3 Per Protocol Analysis Subset

A per protocol analysis for the primary efficacy endpoint will also be implemented and be considered supportive to the primary analysis based on the primary efficacy analysis subset. The per protocol analysis subset will include all subjects in the primary efficacy analysis subset who received at least 5 of the 6 planned doses and who had no important protocol deviations through Month 6. Partial dose is considered as missing dose in per protocol analysis subset. Subjects who received the incorrect treatment (compared to their randomized treatment) at any time point will be excluded from this subset. The important protocol deviations will be identified prior to the primary analysis. Subjects will be analyzed according to their randomized treatment group.

6.4 Pharmacokinetic Analysis Subset

The pharmacokinetic analysis subset includes all randomized subjects who received at least 1 dose of IP and have at least 1 reported pharmacokinetic concentration result. Subjects will be analyzed according to their actual treatment received.

7. Planned Analyses

7.1 Interim Analysis and Early Stopping Guidelines

No interim analyses or sample size re-estimation are planned for this study.

7.2 Primary Analysis

The primary analysis will be performed after all subjects have had the opportunity to complete the Month 6 visit. Only data from the 6-month treatment period will be summarized for the primary analysis. The primary objective of the primary analysis is to evaluate the noninferiority of the effect of self-administering 210 mg romosozumab QM via AI/Pen compared with the effect of 210 mg romosozumab QM administered by HCP via PFS in postmenopausal women with osteoporosis with respect to percent change from baseline in DXA BMD of lumbar spine at Month 6. Formal statistical testing will be conducted to evaluate the following hypothesis: the mean percent change from baseline in lumbar spine DXA BMD at Month 6 in subjects self-administering 210 mg romosozumab QM with AI/Pen is not inferior to that in subjects receiving 210 mg

romosozumab QM by HCP administration with PFS using a margin of -2 percentage points. The lower bound of the 1-sided 97.5% CI from mean treatment difference (self-administration with AI/pen minus HCP administration with PFS) for the treatment arms will be compared with the noninferiority margin of -2% for assessing noninferiority.

Secondary objectives of the primary analysis include the evaluation of the efficacy of self-administration of 210 mg romosozumab QM by AI/Pen and HCP administration of 210 mg romosozumab QM by PFS on the following:

- percent change from baseline in DXA BMD of total hip and femoral neck at Month 6

[REDACTED]

[REDACTED]

Safety objectives of the primary analysis include the comparison of safety and tolerability of self-administration of 210 mg romosozumab QM by AI/Pen and HCP administration of 210 mg romosozumab QM by PFS on the following:

- subject incidence of treatment-emergent adverse events
- subject incidence of the formation of anti-romosozumab antibodies
- change from baseline in laboratory assessments and vital signs

The focus of the safety statistical analyses will be descriptive. No formal statistical testing will be performed.

7.3 Final Analysis

The final analysis will be performed after all subjects have had the opportunity to complete the Month 9 visit, ie, after all subjects have had the opportunity to complete the 3-month follow-up study period. Cumulative safety data from the 6-month treatment and follow up periods will be summarized for the final analysis. The 3-month follow-up period will provide the opportunity to monitor all subjects for adverse events and formation of anti-romosozumab antibodies.

The primary objective of the final analysis is the safety objective, ie, the comparison of the safety and tolerability of a 6-month treatment with 210 mg romosozumab at 90 mg/mL QM by HCP administration with PFS or by subject self-administration with AI/Pen.

The focus of the safety statistical analyses will be descriptive. No formal statistical testing will be performed.

8. Data Screening and Acceptance

8.1 General Principles

The objective of the data screening is to assess the quantity, quality, and statistical characteristics of the data relative to the requirements of the planned analyses.

8.2 Data Handling and Electronic Transfer of Data

The Amgen Global Study Operations-Data Management department will provide all data to be used in the planned analyses. This study will use the RAVE database.

8.3 Handling of Missing and Incomplete Data

Subjects may have missing specific data points for a variety of reasons. In general, data may be missing due to a subject's early withdrawal from study, a missed visit, or non-evaluability of a specific clinical measurement at its planned clinical visit. Unless specified, no imputation will be used. The general procedures outlined below describe the procedures when a data point is missing.

8.3.1 DXA BMD Endpoints

Lumbar spine scans at screening and Month 6 will be acquired in duplicate. The average of the duplicate scans on the same day will be used for analyses. For proximal femur DXA scans, the left side should be used for all scans at all study visits. If the right side must be used (eg, due to implants) or is inadvertently used at baseline, then it must be used consistently throughout the study.

For the primary analysis, missing baseline BMD by DXA at any anatomical site will not be imputed. For purposes of the primary efficacy endpoint analysis and secondary efficacy analyses, observed BMD data at month 6 will be used in the analysis of covariance (ANCOVA) models. If a subject has BMD values from different DXA machine types (ie, Hologic and Lunar) only those BMD values that are collected from the same machine type as the baseline BMD will be used for analyses. For proximal femur scans that are measured on different body sides (i.e., left and right), only those BMD values that are collected from the same body site as the baseline BMD will be used for analyses.

A sensitivity analysis will be performed using multiple imputation to evaluate the primary and secondary endpoint analyses. In this analysis, the missing baseline or Month 6 DXA values will be imputed separately resulting in 5 complete sets by Markov Chain Monte Carlo (MCMC) method for each endpoint. The imputation model will include the baseline value, machine type, and treatment group.

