10.2.4.1 DXA BMD Endpoints

Missing baseline values for endpoints by DXA at any anatomical site will not be imputed. Sensitivity analysis accounting for missing data will be described in the statistical analysis plan.

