3.2 Sample Size

The noninferiority margin is calculated on the basis of the comparison of 210 mg romosozumab at a 90 mg/mL concentration administered QM by an HCP using PFS with placebo on percent change from baseline in lumbar spine at Month 6 in postmenopausal women with low bone mass (Study 20120156).

[REDACTED]

[REDACTED]

[REDACTED]

[REDACTED]

[REDACTED] This result assumes a 5% dropout rate during the 6-month treatment period, no expected difference in mean percent changes in lumbar spine DXA BMD from baseline at Month 6 between the 2 groups, and a common standard deviation of 4.3 percentage points.

4. Covariates and Subgroups

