9.5.1 Analyses of Primary Efficacy Endpoint

The primary analysis to assess the percent change from baseline in DXA BMD at lumbar spine at Month 6 will employ an analysis of covariance (ANCOVA) model using observed data. The ANCOVA model will include randomized treatment, baseline value of BMD, machine type, and interaction of baseline BMD value and machine type as prognostic variables. Summaries for the results will include least-squares means point estimates of the percent change from baseline for each treatment arm. The model will allow for heterogeneity between treatments. The 2-sided 95% CI and associated p-value will be provided for the difference between the least-squares means for HCP-administered 210 mg romosozumab by PFS and self-administered 210 mg romosozumab by AI/Pen.

Conclusions for the primary efficacy hypothesis of efficacy of self-administration of romosozumab by AI/Pen compared with HCP-administered romosozumab by PFS at lumbar spine BMD at Month 6 will be made using a 1-sided test with type 1 error rate of 0.025 and noninferiority margin of -2.0%. The primary efficacy analysis set will be used

In addition, summaries of treatment-emergent adverse events occurring in at least 5% of the subjects and serious adverse events occurring in at least 0.1% of the subjects by preferred term in any treatment arm will be provided in descending order of frequency.

Summaries of treatment-emergent and serious adverse events will be tabulated by system organ class, preferred term, and grade.

Subject incidence of disease-related events will be summarized for all treatment-emergent disease-related events and fatal disease-related events by system organ class and preferred term.

The subject incidence of treatment-emergent adverse device effects will also be summarized.

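### SAP 8.3.1 imputes missing baseline BMD in the sensitivity analysis, which the protocol rules out, without recording the change or saying that Month 6 BMD is in the imputation model; it also uses only 5 sets

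*SAP*

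**What the plan says.** Protocol 10.2.4.1 states: "Missing baseline values for endpoints by DXA at any anatomical site will not be imputed". Its next sentence leaves the sensitivity analysis for missing data to the SAP.

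SAP 8.3.1 keeps the ban on imputing baselines for the primary analysis, which uses observed Month 6 data. It then adds a multiple-imputation sensitivity analysis for the primary and secondary endpoints, in which "the missing baseline or Month 6 DXA values will be imputed separately resulting in 5 complete sets by Markov Chain Monte Carlo (MCMC) method"; the sentence goes on to say that this is done for each endpoint. The model is described in one line: "The imputation model will include the baseline value, machine type, and treatment group". Month 6 BMD is not named.

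The analysis model in SAP 9.5.1 also contains the "interaction of baseline BMD value and machine type as prognostic variables", which the imputation list lacks. The primary conclusion comes from that observed-data ANCOVA, by a "1-sided test with type 1 error rate of 0.025 and noninferiority margin of -2.0" percent.

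SAP Section 10, which lists changes from the protocol, covers the direction of the treatment difference and the uncollected Month 3 height and weight. It does not mention baseline imputation. The SAP's amendment log shows that the amendment put the words 'baseline or' into a sentence that had covered Month 6 only, and left the list of model variables as it was.

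**The concern.** There are three separate issues.

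First, the protocol sentence has no exception for sensitivity analyses, the SAP does what that sentence excludes, and the section meant for such differences is silent.

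Second, the variable list suits the imputation of Month 6 from baseline. It does not suit the reverse. For a woman without a baseline, the list leaves only machine type and treatment. Her percent change would then be her real Month 6 BMD set against a baseline drawn as if for another woman on the same type of scanner. Most of the resulting spread would come from differences between women, not from treatment response.

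Third, 5 imputed sets leave the lower confidence limit partly dependent on the random seed.

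At stake is the credibility of the only missing-data check visible in the public SAP for a noninferiority claim. The per-protocol analysis in SAP 6.3 does not address missing scans. A check that fails because of imputation noise says nothing about missing data.

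**Working it through.** **Inputs from the documents.** About 260 women randomized 1:1 (protocol 5.2); "a common standard deviation of 4.3 percentage points" and 5% dropout (SAP 3.2); true difference 0 (SAP 3.2); margin -2 points, one-sided 0.025 (SAP 7.2 and 9.5.1); mean 6-month spine gain 9.7% (protocol 5.4).

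**Assumptions.** Power is redacted; 95% is assumed. Between-woman coefficient of variation (CV) of spine BMD within machine type 10% to 15%; half the women on each machine type, with a 15% offset between types; data missing at random; k women with Month 6 but no baseline.

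**1. The plan's own size.** n per arm = 2 × (1.960 + 1.645)² × 4.3² / 2² = 120.1, so 121. With 5% dropout, 121 / 0.95 = 127.4, so 128 per arm and 256 in total, close to 260. Powers of 90% and 96% give 208 and 270, so 95% fits best.

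**2. Expected precision.** Evaluable per arm: 130 × 0.95 = 123.5. SE = 4.3 × √(2/123.5) = 0.547. Lower limit at zero difference = -1.96 × 0.547 = -1.07, which is 0.93 points above the margin. The SE would have to reach 2 / 1.96 = 1.02 for that limit to touch -2.

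**3. One literally imputed baseline.** To first order, the drawn baseline alone contributes 109.7 × CV points: 11.0 at CV 10%, 16.5 at 15%. Because her Month 6 value varies independently of the draw, this is multiplied by √2, giving 15.5 and 23.3. Adding the ordinary 4.3 in quadrature gives an SD of about 16.1 and 23.7 points, instead of 4.3.

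**4. Effect on the SE, by hand, for k = 3.**
- CV 10%: average variance = 18.49 + (3/247)(259.2 - 18.49) = 21.4. Within-imputation variance = 2 × 21.4 / 123.5 = 0.347. Between-imputation variance = 3 × (10.97/123.5)² = 0.0237. Rubin's rules with 5 sets: √(0.347 + 1.2 × 0.0237) = 0.61.
- CV 15%: average variance = 18.49 + (3/247)(560.0 - 18.49) = 25.1; within = 0.406; between = 3 × (16.46/123.5)² = 0.0533; SE = √(0.406 + 1.2 × 0.0533) = 0.69.

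**5. Simulation.** 1,500 trials per setting, 260 women, 13 missing Month 6, the planned ANCOVA with variance by arm, 5 sets. Ranges run over CV 10% to 15%. 'Reversed' is the share of trials passing the primary analysis in which the imputation check fails.

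| Baseline drawn from machine type and treatment only | SE | Mean lower limit | Reversed |
|---|---|---|---|
| k = 0 | 0.55 to 0.56 | -1.10 to -1.12 | under 1% |
| k = 1 | 0.58 to 0.61 | -1.14 to -1.20 | 2% to 5% |
| k = 2 | 0.60 to 0.66 | -1.17 to -1.32 | 2% to 8% |
| k = 3 | 0.62 to 0.70 | -1.26 to -1.37 | 5% to 14% |
| k = 13 | 0.79 to 1.04 | -1.59 to -2.14 | 22% to 54% |

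The hand figures of 0.61 and 0.69 agree with the k = 3 row. With Month 6 BMD in the baseline imputation, or with baselines not imputed, k = 1 to 3 gives SE 0.555 to 0.560, a mean limit of about -1.1 and about 1% reversed.

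**6. Number of sets.** Take missing information of about 5% and SE 0.545. Between-imputation variance = 0.05 × 0.545² = 0.0149. Seed SD of the estimate = √(0.0149/5) = 0.055 with 5 sets and √(0.0149/50) = 0.017 with 50. Repeated seeds in simulation gave about 0.06 and 0.02 for the lower limit.

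**The case against.** The literal reading is probably not what was meant. A reader might take 'separately' to mean that baselines are drawn apart from Month 6. But the sentence ends by referring to each endpoint, and the superseded SAP text in the amendment log used the same word when only Month 6 was imputed. It most likely means separately for spine, total hip and femoral neck. One MCMC model that imputes Month 6 must also contain Month 6, listed or not, and would then draw a missing baseline given the woman's Month 6 value. This stands, and it makes the noise in steps 3 to 5 conditional on the less likely reading. It does not settle what the SAP says, because the listed variables still omit Month 6 BMD.

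Missing spine baselines should also be rare. Screening scans are analysed centrally, two evaluable vertebrae are required, re-scans can be requested, and a scan up to Study Day 14 counts as baseline. This stands too. A few cases remain possible: eligibility accepts a qualifying T-score at the hip alone, and vertebral evaluability is judged at the site (criteria 105 and 106). The documents give no count.

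A reader might call the SAP a breach of the protocol. That goes too far, because the protocol hands the sensitivity analysis to the SAP. What stands is an unrecorded inconsistency.

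Five sets are already efficient: 1 / (1 + 0.05/5) = 99%. The seed noise of 0.06 is small against the expected gap of 0.93 points and matters only for a limit close to -2.

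Finally, the public text of SAP 9.5.1 breaks off where the primary analysis set is described, so further sensitivity analyses may be specified there.

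**Conclusion.** The inconsistency holds, and so does the gap in the model description. SAP 8.3.1 imputes baselines that protocol 10.2.4.1 says will not be imputed, SAP Section 10 does not say so, and the listed variables do not make clear that a woman's own Month 6 BMD informs her imputed baseline.

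On the literal list, 1 to 3 affected women would raise the SE from about 0.55 to between 0.58 and 0.70 and reverse about 2% to 14% of primary passes. On the joint reading there is no such effect. These figures rest on the assumed CV of 10% to 15% and on assumed counts.

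A reader might infer that a few women without a baseline would overturn noninferiority. The documents and figures do not support that. With 1 to 3 such women the mean lower limit stays between -1.14 and -1.37. Reversal becomes more likely than not only at about 13 women with CV 15%, and does not do so even at 20 with CV 10%. The primary conclusion uses observed data and is untouched. The added noise makes the supportive check harder to pass, so it does not help to produce a false claim of noninferiority.

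The number of sets is a minor, separate point. The effect of leaving the baseline-by-machine-type interaction out of the imputation was not sized.

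**What to change.** In SAP 8.3.1, do one of the following:

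- Delete 'baseline or', so that only Month 6 is imputed, as the protocol sentence implies. The existing variable list then fits its purpose.
- Keep baseline imputation, but state that baseline and Month 6 BMD are imputed jointly on the BMD scale with treatment and machine type, and that percent change is computed afterwards. Imputing within machine type would match the interaction in the analysis model.

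In either case use at least 50 sets, and list any departure from protocol 10.2.4.1 in SAP Section 10.

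The cost is a few words and slightly more computing time. If baselines are not imputed, the few women without one stay out of the sensitivity analysis, as they already do from the primary analysis.

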4.1 Planned Covariates

All analyses assessing treatment effect of BMD will include randomized treatment, baseline BMD at the same body site as the endpoint, machine type, and interaction between baseline BMD and machine type as prognostic variables in the model.

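### The multiple-imputation sensitivity analysis of BMD uses only 5 imputed data sets, which leaves small but avoidable Monte Carlo error in a supportive result

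*SAP*

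**What the plan says.** SAP 8.3.1 states: "A sensitivity analysis will be performed using multiple imputation to evaluate the primary and secondary endpoint analyses". When a scan result is absent at either time point, the plan is that it "will be imputed separately resulting in 5 complete sets by Markov Chain Monte Carlo (MCMC) method for each endpoint". On the variables used, it adds: "The imputation model will include the baseline value, machine type, and treatment group". The visible text gives no seed and no target for Monte Carlo error.

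The main analysis is separate. Under SAP 9.5.1 it "will employ an analysis of covariance (ANCOVA) model using observed data", and the conclusion rests on a "1-sided test with type 1 error rate of 0.025 and noninferiority margin of -2.0" percent. No imputation enters it. A per protocol analysis is a second supportive analysis of the primary endpoint (SAP 6.3; Protocol 10.3.2.2).

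**The concern.** With multiple imputation, the pooled estimate is an average over random draws, and the between-imputation variance is itself estimated from those draws. With 5 sets that variance rests on 4 degrees of freedom. Two analysts with the same data, model and code but different seeds will report different lower limits.

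A missing-data sensitivity analysis is read by asking whether its lower limit still lies on the same side of the margin as the main result. Movement caused by the seed blurs that reading, most of all when the limit is close to -2. If the seed is not fixed in advance, its choice is also left open in an open-label trial.

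**Working it through.** **Inputs from the documents.** Margin -2 and one-sided alpha 0.025 (SAP 9.5.1); "a common standard deviation of 4.3 percentage points" and zero expected difference (SAP 3.2); about 130 per arm (Protocol 5.2); 5 imputed sets (SAP 8.3.1). For missingness, SAP 3.2 says: "This result assumes a 5% dropout rate during the 6-month treatment period". That 5% is used here as the share of missing Month 6 scans. The true share could be lower, because subjects who leave early should have the Month 6 procedures (Protocol 9.1.2) and Appendix A of the SAP counts any scan from Study Day 2 as Month 6. It could be higher, because scans on a different machine type from baseline are dropped (SAP 8.3.1). Rates of 10% to 20% are assumptions.

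**The plan's sample size.** The power target is blacked out, so 260 can only be checked against assumed targets. Per arm, n = 2 × (4.3/2)² × (z for 0.975 + z for power)².
- At 95% power: 9.245 × (1.960 + 1.645)² = 120.1, so 121; 121/0.95 = 127.4, so 128 per arm and 256 in total.
- At 90% power the same steps give 208.

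The inputs therefore fit about 260 if the target was 95%, which the documents do not confirm.

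**Room above the margin.** With 5% missing, 130 × 0.95 = 123.5 per arm are evaluable.
- SE = 4.3 × √(2/123.5) = 0.547.
- Expected lower limit at zero difference = -1.97 × 0.547 = -1.08.
- Distance to the margin = 2 - 1.08 = 0.92 points.

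**Seed error, closed form.** The SD of the pooled estimate due to the seed is about SE × √(missing fraction/m), where m is the number of sets.
- m = 5: 0.547 × √(0.05/5) = 0.055.
- m = 100: 0.547 × √(0.05/100) = 0.012.
- Ratio: √(100/5) = √20 = 4.5.

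**Seed error, simulation.** Month 6 values were imputed from baseline, machine type and treatment, analysed by the ANCOVA with the baseline-by-machine interaction, and pooled by Rubin's rules with small-sample degrees of freedom. Data were held fixed and only the seed changed (300 seeds on each of 8 data sets). Assumptions not in the documents: random missingness equal in both arms, equal variances, no missing baselines, an even machine mix and a normal baseline BMD. Whole subjects had to be removed, so the 5% case has 6 missing per arm (0.05 × 130 = 6.5).

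| Missing | SD of lower limit, 5 sets | SD, 100 sets |
|---|---|---|
| 5% | 0.059 | 0.013 |
| 10% | 0.093 | 0.020 |
| 15% | 0.141 | 0.027 |
| 20% | 0.163 | 0.032 |

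The limit moves slightly more than the estimate because the pooled variance also changes with the seed. At 5% missing, the middle 95% of seeds spans about 0.23 points with 5 sets and 0.05 with 100. An SD of 0.059 is about 11% of the SE (0.059/0.547) and 6% of the distance to the margin (0.059/0.92).

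**How often two seeds fall on opposite sides of -2** (3,000 simulated trials per setting for 5 sets, 1,500 for 100). The true difference of -0.93 is an assumption chosen to put the expected limit at the margin: -0.93 - 1.08 = -2.01.

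| Missing | True difference | 5 sets | 100 sets |
|---|---|---|---|
| 5% | 0 | 1.4% | 0.3% |
| 10% | 0 | 2.4% | 0.5% |
| 20% | 0 | 5.9% | 1.1% |
| 5% | -0.93 | 4.7% | 1.1% |
| 10% | -0.93 | 7.5% | 1.4% |
| 20% | -0.93 | 11.6% | 2.7% |

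**The case against.** The strongest reply is that this is a supportive analysis in which the effect is small. Under the plan's own assumptions the limit sits 0.92 points above -2 and the seed moves it by about 0.06, so the reading would almost never change. The SAP also states no pass/fail rule against -2 for the imputed analysis; the opposite-sides comparison is this review's yardstick. All of this stands, and it sets the weight of the point. It is not a reason to keep 5 sets, since more sets cost nothing of substance.

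Four stronger readings are tempting, and the documents do not support them:
- *The noninferiority conclusion depends on the seed.* It does not. That conclusion comes from the ANCOVA on observed data.
- *This is the only check for missing data.* That cannot be confirmed. In the public text SAP 9.5.1 breaks off and resumes within 9.6.1, and the Protocol synopsis is blacked out right after the per protocol analysis. A seed or a further sensitivity analysis may be stated there.
- *One hundred sets remove the problem.* They reduce the seed error about 4.5-fold; an SD of about 0.013 points remains at 5% missing.
- *The imputation model contradicts SAP 4.1.* That section requires the "interaction between baseline BMD and machine type as prognostic variables in the model" for analyses that assess the treatment effect. It sets no rule for the imputation model. Imputing under a model simpler than the ANCOVA is a matter of good practice, with an effect that is expected to be small and was not quantified.

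**Conclusion.** The point holds as a free improvement. Five sets give the pooled lower limit a seed-to-seed SD of about 0.06 points under planned conditions, and 100 sets bring this to about 0.013. The practical consequence is slight if missingness is near 5% and the arms do not differ. It becomes noticeable only with missingness well above plan or a limit near -2, neither of which the documents predict.

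The figures rest on the simplified simulation described above. SAP 8.3.1 also imputes missing baselines and SAP 9.5.1 allows unequal variances; neither was modelled. The agreement with the closed form suggests that the size is right for the Month 6 component.

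**What to change.** In SAP 8.3.1, raise the number of imputed data sets from 5 to at least 100 and state the random seed in advance. The two changes do different jobs: more sets reduce the Monte Carlo error, while a fixed seed makes the run repeatable without making it more precise.

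Optionally, add the baseline-by-machine-type interaction to the imputation model, or impute within machine type, so that it is no simpler than the ANCOVA.

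The cost is a sentence or two in the SAP and seconds of computing. No subjects, visits or data are added, and the primary analysis stays as it is.
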